9.4. Determination of Sample Size

The sample size for the study was calculated assuming an estimand of the effect size between active treatment and placebo of 0.51 on both endpoints, considering the placebo effect will not exceed the 30%.

The Phase IIa REIMAGINE trial did not contain a placebo group to further help establish the estimand. Moreover, there is no 'gold standard' measure in BPD clinical development, thus, there is no historical clinical trial data on the COAs proposed in PORTICO to establish a more accurate estimand.

Controlling the overall type I error rate at 5% for the study, both endpoints will be tested at a two-sided alpha of 2.5%. A power of approximately 80% for each endpoint is achieved with 75 patients completing the study in each arm, active treatment and placebo. Accounting for a drop-out rate of 20%, 94 patients (total 188 patients) should be recruited per arm. A sample size adjustment will be considered at the interim analysis (see Section 9.6). The total sample size will not be increased to more than 300 completed patients.

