4.7 Determination of Sample Size

The sample size for the study was calculated assuming an effect size of 0.51 on both endpoints between active treatment and placebo. Controlling the overall type I error rate at 10% for the study, each endpoint will be tested at a two-sided alpha of 5% (equivalent to 2.5% one-sided) considering that a significantly larger decrease compared to placebo in either endpoint will be considered sufficient for study success. A power of approximately 80% for each endpoint is achieved with 62 patients completing the study in each arm, active treatment, and placebo. Accounting for a drop-out rate of 20%, 78 patients (total 156 patients) should be recruited per arm. A sample size adjustment will be considered at the interim analysis (see Section 9.6).

The original sample size adjustment above controls the overall type 1 error rate at 10%. However, to meet the requirements for proof of registration, the alpha was adjusted to control for a type 1 error rate of 5%, split evenly between the two endpoints. Assuming an effect size of 0.51 (mean 510, standard deviation 1000) a sample size of 150 completers (75 per arm) is required for 80% power at a two-sided alpha of 0.025 for each endpoint. Assuming 20% dropout would require 188 patients enrolled.

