Figure 2. Promising Zone. The promising zone boundaries (orange box) and corresponding sample size increases are detailed above. The solid black line corresponds to the proposed enrolled (right; y-axis) and completer (left; y-axis) sample sizes relative to the test statistic (x-axis) observed at interim. Sample sizes were calculated using an 80-85% power threshold to provide binning for sample size increase, thus avoiding back calculation of the effect size at interim. Unfavorable and favorable zones are shaded in grey and blue, respectively.

The conditional power at interim, or probability of study success, for detecting the difference in primary outcome between the two groups in the final analysis, will be estimated using the accumulated data. The proposed starting sample size of 90 study participants results in 85% power for both primary outcomes (assuming a Cohen's D of 0.51). We have elected to begin the study

with the expected sample size estimate and adjust upward if improvement in the treated cohort does not resemble what was observed in the previous studies.

The promising zone will increase the sample size to maintain 80% to 85% power to detect a significant effect, i.e. if the power goes below 80% the sample size will be increased to achieve power between 80% and 85% (Table 1; Figure 2). Development of the 80-85% thresholds also maintain blind of the interim results. If at interim the test statistic is in the favorable zone (≥ 1.944) the study will proceed as originally described (150 completers). If at interim the test statistic falls within the promising zone (test statistic: $< 1.944 \geq 1.412$), sample size adjustment will follow the test statistic ranges outlined in Table 1 and Figure 1. If the test statistic is less than 1.412 (40% conditional power at interim) the sample size will not be increased (remain at 150 completers). The lower bound of the promising zone (effect size 0.23) is set by sample size constraints, however clinically meaningful effects have been observed at an effect size as low as 0.2. The study will be stopped for futility if the test statistic falls below a 50% probability (conditional power) of observing a result favoring *placebo*. This corresponds to a test statistic below -1.987 (effect size equal to -0.4177).

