At interim analysis two discontinued individuals reached visit 6, and were included in the IA analysis. The table below was adjusted for 92 individuals worth of information, as opposed to the 90 individuals mentioned above.

Table 1. Promising Zone Thresholds

	Test Statistic at Interim	Completers	Sample Size (total Enrollment)
Futility	$-\infty < Z \leq -1.987$	N at time of futility declaration	--
Unfavorable Zone	$-1.987 < Z < 1.412$	150	188
Promising Zone	$1.412 \leq z < 1.555$	300	376
	$1.555 \leq z < 1.649$	265	332
	$1.649 \leq z < 1.745$	231	290
	$1.745 \leq z < 1.845$	201	252
	$1.845 \leq z < 1.944$	174	218
Favorable Zone	$1.944 \leq z < \infty$	150	188

Sample size calculations will be generated as described below. The more conservative sample size calculation between the two primary efficacy endpoints will be used.

The following formulas will be used:

$$CP(z_1, \tilde{n}_2) = 1 - \Phi \left(\frac{z_\alpha \sqrt{n_2} - z_1 \sqrt{n_1}}{\sqrt{\tilde{n}_2}} - \frac{z_1 \sqrt{\tilde{n}_2}}{\sqrt{n_1}} \right)$$

$$\tilde{n}_2' = \left(\frac{n_1}{z_1^2} \right) \left(\frac{z_\alpha \sqrt{n_2} - z_1 \sqrt{n_1}}{\sqrt{n_2} - n_1} + z_\beta \right)^2$$

Here:

- z_1 is the Wald-statistic observed at the interim analysis,

- α is the *one-sided* significance level of the test (here 2.5%),
- z_{α} is the corresponding critical value of the normal distribution,
- n_2 is the total number of patients originally planned,
- \tilde{n}_2 is the incremental number of patients $n_2 - n_1$,
- \tilde{n}_2' is the proposed new incremental number of patients,
- β is 1 - statistical power, and
- Φ is the cumulative density function of the normal distribution.

Note: \tilde{n}_2' will only be calculated if CP is in the promising zone. Both n_2 and the adapted sample size $n_2' = n_1 + \tilde{n}_2'$ are adjusted for the expected drop-out rate, i.e., the n_2 is considered to be 150 and $n_2 / 0.8$ patients (rounded up to an even number) will be recruited after adaptation of the sample size.

If the CP for both endpoints is below 40%, the study will be continued without modifications.

Details for the safety deliverables are described in Section 5.2.11.

All analyses at interim will be conducted by a separate unblinded statistical team.

The decision tree for promising zone can be found in appendix 7.3.

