4.12 Multiple Comparisons/Multiplicity

There are two primary endpoints for efficacy analysis: CGI S A/A and BPDCL, a significant difference in either one is considered sufficient for study success. The overall significance level of the study is thus strictly controlled at a level of 5%. The Hochberg correction will be applied. If one endpoint is below the 2.5% level or if both endpoints are below the 5% level of significance the study is declared a success.

5 Efficacy Evaluation

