Sites with less than two study participants per arm will be pooled. To pool sites: sites with less than two study participants per arm will be ranked within country by the number of participants within the placebo arm (higher numbers are ranked higher). Ranked sites will be pooled starting by pooling the highest ranks until the study participant requirement per arm is met. If more sites are present after the pooling criterion is met the remaining sites are pooled to meet the criterion. In the event that remaining sites do not meet the criterion they will be combined with the previously pooled group. In the event of a tie for ranking the sites, the site with the largest number in the active arm will be used. If the tie persists the sites will be ordered alphabetically or numerically (A and higher number result in a higher rank). Due to the small sample size the interim analysis will be ranked across all sites for pooling as opposed to within country.

Pooling at interim will not include country due to the small number of individuals.

The primary treatment contrast will be based on the LS means from the treatment by visit interaction term. A contrast statement will be written such that model estimates from assessments collected between weeks 8-12 are averaged to compare drug vs placebo.

The test will be a two-sided test of the null hypothesis of no difference between active treatment and placebo at *Weeks 8-12*.

A listing by subject of the CGI-S A/A scores including changes from baseline will be provided.

Individuals with no post-baseline information will have the first post-baseline visit imputed. Individuals reported to drop out for lack of efficacy will be given the baseline placebo mean. Individuals reported as dropping out for any other reason will be given the baseline group mean of their corresponding treatment.

Reasons not associated with lack of efficacy include but are not limited to the following:

- Participant Decision Due to COVID
- Lost to Follow-up
- Adverse Event
- Protocol Deviation
- Physician Decision
- Non-Compliance
- Blood Value During Randomization Visit Was Exclusionary
- Withdrawal by Subject

For the primary efficacy analyses all other missing data will be accounted for using the MMRM estimates.

The analysis of Total BPDCL will not include a categorical summary table.

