7.2 Promising Zone Type 1 Error Rate Simulation

7.2.1 Figure Output

7.3 Promising Zone Decision Tree

- If estimates from both outcomes are in the promising zone and the difference between the suggested sample sizes for completers is greater than 60 individuals then the least conservative sample size (smallest completer sample size) will be reported. Otherwise, the most conservative (largest completer sample size) will be reported.
- If the estimate from one outcome is in the promising zone and the other in the favorable zone and the difference between the suggested sample sizes for completers is greater than 60 individuals then the least conservative sample size (smallest completer sample size/favorable zone (150)) will be reported. Otherwise, the most conservative (largest completer/promising zone sample size) will be reported.
- If the estimate for one outcome falls in the unfavorable zone and one in the promising zone, then the promising zone sample size increase will be reported.
- If the estimate one outcome falls in the promising zone and one in futility, then the promising zone sample size increase will be proposed.
- If the estimates for both outcomes fall in the unfavorable zone, then there is no change in the sample size.
- If the estimate for one outcome falls in the favorable and the other unfavorable zone, then there will be no suggested change in sample size.
- If the estimate one outcome falls below the threshold for futility and the estimate for the other outcome falls in the unfavorable zone, then there will be no suggested change in sample size.
- If the estimates for both outcomes fall in the favorable zone, then there will be no suggested change in sample size.
- If the estimate for one outcome falls below the threshold for futility and the other is in the favorable zone, then there is no change in the sample size.
- If the estimates for both outcomes are below the threshold for futility, then the algorithm will recommend stopping for futility.

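### SAP 4.8 computes conditional power per endpoint at z = 1.96, so its 40% and 80–85% figures are too high when one endpoint has to win alone at z = 2.241

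*SAP*

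**What the plan says.** **Interim formula.** SAP 4.8 defines α in the conditional-power and re-estimation formulas as the one-sided "significance level of the test (here 2.5"%). The text equates conditional power with the probability of study success and attaches 40% to the lower bound, z = 1.412. It then says: "The promising zone will increase the sample size to maintain 80% to 85% power to detect a significant effect".

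**Sizing.** SAP 4.7 states that 150 completers "is required for 80% power at a two-sided alpha of 0.025 for each endpoint". Protocol 9.4 agrees: "both endpoints will be tested at a two-sided alpha of 2.5"%.

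**Success rule.** SAP 4.12, with the same rule in SAP 4.6 and Protocol 9.3.4: "If one endpoint is below the 2.5% level or if both endpoints are below the 5% level of significance the study is declared a success". SAP 5.1.1 fixes the sidedness: "The test will be a two-sided test of the null hypothesis of no difference".

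**Who triggers an increase.** Appendix 7.3 covers the case in which one outcome "falls in the unfavorable zone and one in the promising zone, then the promising zone sample size increase will be reported". It does the same when the other outcome is in the futility range. When one outcome is favorable and the other unfavorable, the size stays at 150 completers.

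**The concern.** The interim rule and the final rule use different bars for the same endpoint. Two-sided 2.5% is one-sided 1.25%, a critical value of 2.241. The interim formula uses 1.96, which Hochberg allows only when both endpoints clear it. A single-endpoint calculation at 1.96 is therefore neither the chance that this endpoint wins alone nor the chance that the study succeeds.

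Table 1 chooses between 188 and 376 enrolled, and its justification is the 40% floor and the 80–85% target. If those figures do not hold in a branch that Appendix 7.3 explicitly provides for, those who relied on them were given too optimistic a picture for that branch. Some trials would be enlarged from below the intended floor. Others would be left at 150 as favorable with well under 80%.

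**Working it through.** **Inputs.** n1 = 92 (SAP 4.8, the stated basis of Table 1). Planned completers 150 (SAP 4.7, 4.8). Row totals 300, 265, 231, 201 and 174 with their z edges (Table 1). Critical value 1.960 (one-sided 2.5%) or 2.241 (one-sided 1.25%). The correlation between endpoints is not given in the documents; 0 to 0.7 is assumed.

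**Formula (SAP 4.8), with N the final number of completers:**

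CP = 1 − Φ[(z_α√N − z1√n1)/√(N − n1) − z1√(N − n1)/√n1]

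For the enlarged rows, N is the row total, with the ordinary Wald test at the end.

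**Step 1: reproduce the plan.** √150 = 12.247, √92 = 9.592, √58 = 7.616.

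- z1 = 1.412 at 1.960: (24.004 − 13.543)/7.616 − 1.121 = 0.252, so CP = 40.0%, as stated.
- z1 = 1.944 at 1.960: (24.004 − 18.646)/7.616 − 1.544 = −0.840, so CP = 80.0%.

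With n1 = 90 the 40% and 80% points would be 1.394 and 1.930, so Table 1 was built with n1 = 92 and z = 1.96.

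**Step 2: the bar for an endpoint that wins alone.**

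- z1 = 1.412 at 2.241: (27.451 − 13.543)/7.616 − 1.121 = 0.705, so CP = 24.0%.
- z1 = 1.944 at 2.241: (27.451 − 18.646)/7.616 − 1.544 = −0.387, so CP = 65.1%.

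| Interim z | Completers | CP at 1.960 | CP at 2.241 |
|---|---|---|---|
| 1.412 | 150 | 40.0% | 24.0% |
| 1.412–1.555 | 300 (cap) | 76.1–84.6% | 64.4–75.2% |
| 1.555–1.649 | 265 | 80.0–85.0% | 68.9–75.5% |
| 1.649–1.745 | 231 | 80.0–85.0% | 68.4–75.0% |
| 1.745–1.845 | 201 | 80.0–85.1% | 67.7–74.5% |
| 1.845–1.944 | 174 | 80.0–85.1% | 66.7–73.5% |
| 1.944 | 150 | 80.0% | 65.1% |

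The 300 row falls short of 80% at its lower edge even at 1.96, because of the 300-completer cap. The uncapped rows give the like-for-like comparison: about 67–75% against 80–85%.

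**Step 3: study-level conditional power under Hochberg.** Success means either endpoint above 2.241 or both above 1.960. The two future increments are taken as bivariate normal, each endpoint continuing at its observed interim effect, with correlation 0 to 0.7.

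| Other endpoint at interim | z = 1.412, N = 150 | Lower edges of the five promising rows | z = 1.944, N = 150 |
|---|---|---|---|
| z = 0 | 24% | 64–69% | 65% |
| z = 1.0 (still unfavorable) | 27–30% | 67–78% | 65–68% |
| Same z as the first | 38–45% | 78–92% | 80–90% |

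**Step 4: sizing check.** At two-sided 0.025 and effect size 0.51, the normal approximation gives 74 per arm, and 81.1% power at the stated 75. The sizing therefore uses 2.241; only the interim section uses 1.96.

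**The case against.** The strongest reply is that Hochberg has a second route. If both endpoints look alike at the interim, 1.96 is close to the relevant bar, and Step 3 shows the stated figures then hold or are exceeded. The design also assumes an effect of 0.51 on both endpoints. On that assumption, with correlation 0.3 to 0.7, when one endpoint is promising the other is at or above 1.412 in about 76–80% of cases, and at or below zero in about 1% or less. This stands. A reader might infer that every power in Table 1 is overstated, and the documents do not support that. What remains is the other 20–24% of such cases, a larger share if the drug affects mainly one endpoint, and Appendix 7.3 makes specific provision for them. The shortfall also shrinks as the lagging endpoint approaches the zone: with it at z = 1.3, study-level power at z = 1.412 with 300 completers is 75–81% (correlation 0.3 to 0.7).

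A reader might also infer inflated type I error. The α in 4.8 does not enter the final test, which SAP 4.12 and 5.1.1 define separately. The simulation code that 4.8 cites for error control is not in the documents, so nothing is alleged on that score.

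Finally, one might take the 2.5% as a leftover from the superseded sizing in SAP 4.7, where "each endpoint will be tested at a two-sided alpha of 5% (equivalent to 2.5% one-sided"). That is plausible but unproven: one-sided 2.5% also matches the current overall two-sided 5% and Hochberg's first step.

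**Conclusion.** The concern holds for the case in which one endpoint carries the trial. There, with the lagging endpoint adding little, conditional power is about 24% rather than 40% at z = 1.412. It is about 67–75% rather than 80–85% in the uncapped rows (64–75% in the 300 row, partly because of the cap), and about 65% rather than 80% at z = 1.944. A lagging endpoint at z = 1.0 closes only part of the gap. With both endpoints at the same interim z, the plan's figures are about right or conservative.

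These results rest on the SAP's own formula, the observed interim effect continuing, equal information on both endpoints and an assumed correlation of 0 to 0.7. The defect is a wrong stated power behind a decision threshold. The final test is unaffected.

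**What to change.** SAP 4.8 describes in the past tense which discontinued participants entered the interim analysis, so the interim appears to have been run. In that case:

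- Keep the Table 1 thresholds and sizes.
- Restate the conditional powers in 4.8 and Figure 2 as (a) endpoint-wins-alone values at z = 2.241 and (b) study-level values under the Hochberg rule over a stated range of endpoint correlation.
- Correct the definition of α, and say which success event each figure refers to.

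This costs a text and figure revision, with no extra patients and no change made after an unblinded look.

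Only if no interim decision has been taken should the thresholds be recomputed, preferably on the Hochberg success rule. The alternative is one-sided 1.25% for the branches where one endpoint stands alone (bounds 1.632 and 2.165, cap of 300 unchanged). Applying 2.241 in every branch would ignore the both-below-5% route. Either recomputation requires the type I error simulation to be rerun.

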4.9 Demographic and Other Baseline Characteristics

Demographics will be based on the SAF. The following summaries will be produced:

- A summary of demographic variables (e.g., age, sex, race, height, and weight) by treatment and overall
- A summary of disease background factors, including whether patient is in psychotherapy at the start of the study
- A summary of the medical history, by System Organ Class and Preferred Term

Demographics and baseline characteristics will also be listed by patient.

The answers to the Mini-International Neuropsychiatric Interview (MINI) will be listed, and the primary diagnosis will be summarized as part of the disease background factors table.

4.10 Concomitant Medication

Medication start and stop dates will be compared to the date of first dose of study medication to allow medications to be classified as either Prior only, both Prior and Concomitant, or Concomitant only. Medications starting after the completion/withdrawal date will be listed but will not be classified or summarized.

Medications that start and stop prior to the date of first dose of study medication will be classified as Prior only. If a medication starts before the date of first dose of study medication and is either ongoing or stops on or after the date of first dose of study medication, then the medication will be classified as both Prior and Concomitant. Medications will be classified as Concomitant only if they have a start date on or after the date of first dose of study medication.

If medication start and/or stop dates are missing or partial, the dates will be compared as far as possible with the date of first dose of study medication. Medications will be assumed to be Concomitant only, unless there is clear evidence (through comparison of partial dates) to suggest that the medication started prior to the first dose of study medication. If there is clear evidence to

suggest that the medication started prior to the first dose of study medication, the medication will be assumed to be both Prior and Concomitant, unless there is clear evidence to suggest that the medication stopped prior to the first dose of study medication. If there is clear evidence to suggest that the medication stopped prior to the first dose of study medication, the medication will be assumed to be Prior only.

Prior and Concomitant medications will be coded according to WHO Drug Dictionary.

Summaries of both Prior and Concomitant medication will be provided for the SAF analysis set by actual treatment arm, displaying the number of percentage of subjects being treated with each type of medication/therapy classified according to ATC level 2 (therapeutic main group) and ATC level 3 (pharmacological subgroup). An additional summary will be created for only prohibited medication (as per Table 2 of the CSP).

A similar summary will be provided for Prior medication.

Medication will also be listed, including classifications, start and end dates, indication, frequency and dose as well as other available variables.

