5.4. Post-study Access to IMPs

Post-study access to the IMP will not be available.

6. Prior and Concomitant Therapy

Prior medication is defined as medication received prior to first IMP intake. Any medication received at least once after the first IMP intake will be considered as concomitant medication.

All prior medications taken within four weeks prior to screening will be recorded in the eCRF at Visit 1.

Concomitant medication will be recorded in the concomitant medication log/page of the eCRF throughout the study. Prior to initiating a new concomitant medication, participants should check with their study doctor.

Participants will be asked to maintain a stable regimen of background pharmacological therapy, not to initiate any prohibited medications during the trial and to advise their study physician of any medication changes throughout the study.

Psychotherapy treatment should also be registered in the eCRF.

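### SAP 4.10 classes a drug recorded at Visit 1 as already taken, but with an unresolvable start date, as Concomitant only, and so leaves it out of the Prior medication summary

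*SAP*

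**What the plan says.** SAP 4.10 sorts medications into three classes by comparing their dates with the date of first dose: Prior only, both Prior and Concomitant, and Concomitant only. With complete dates the scheme is clear. A drug that began before first dose and is ongoing, or stopped on or after it, falls in the middle class: "the medication will be classified as both Prior and Concomitant". The third class is reserved for on-study starts: "Medications will be classified as Concomitant only if they have a start date on or after the date of first dose of study medication".

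When a start or stop date is missing or partial, dates are compared as far as possible, and then a default applies: "Medications will be assumed to be Concomitant only, unless there is clear evidence (through comparison of partial dates"), that evidence having to show a start before first dose. A separate sentence covers stops and again asks for clear evidence; its operative words are: "suggest that the medication stopped prior to the first dose of study medication, the medication will be assumed to be Prior only". After the main medication summaries the section adds: "A similar summary will be provided for Prior medication". The listing is to show each record's class.

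Protocol section 6 works from receipt of the drug, not from a start date: "Prior medication is defined as medication received prior to first IMP intake", and "Any medication received at least once after the first IMP intake will be considered as concomitant medication". It also says when prior drugs are captured: "All prior medications taken within four weeks prior to screening will be recorded in the eCRF at Visit 1".

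**The concern.** Concomitant only amounts to a statement that the drug was begun on or after first dose. The SAP attaches that statement to a drug whose start date nobody could supply, and the one kind of evidence it names for rebutting it is a partial date. Yet the trial collects better evidence. A drug written down at Visit 1 as already being taken was taken before first dose, because first dose is not given until Visit 2.

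The drugs at issue are easy to picture. Protocol 4.1.2 generally allows antidepressants, atypical antipsychotics, mood stabilizers and nootropics if the dose has been stable for at least 2 months before Screening, and inclusion criterion 10 asks for stable background therapy. For such a drug, eligibility itself implies that it pre-dates dosing. If its start date is unresolvable, the listing will nevertheless call it new on study and the Prior summary will not count it. What is at stake is an accurate description of background therapy and a listing that agrees with the protocol's own definitions.

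**Working it through.** No alpha, power or sample size figure depends on this point, and the plan states no number to reproduce. The check is to follow the SAP 4.10 rule through each pattern of dates for a drug recorded at Visit 1 as already taken, and to compare the result with the Protocol section 6 definitions.

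| Pattern | SAP 4.10 class | Protocol section 6 | Agree? |
|---|---|---|---|
| (a) Start unknown; ongoing, or stopped on or after first dose | Concomitant only | Prior and concomitant | No |
| (b) Start unknown, stop unknown | Concomitant only | At least prior | No |
| (c) Start partial, month or year clearly before first dose; ongoing | Both | Prior and concomitant | Yes |
| (d) Start partial, falling in the same month (or, if only the year is known, the same year) as first dose; ongoing | Concomitant only | Prior and concomitant | No |
| (e) Start unknown; documented stop before first dose | Prior only | Prior | Yes |

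In (a) and (d) the concomitant half of the answer is right and the prior half is lost. The record stays in the concomitant summary and the listing, but it does not qualify for the Prior summary and its class says that it began on study.

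Pattern (b) includes a drug that Visit 1 records as already stopped but for which neither date is usable. Date comparison yields nothing, so the default can place it on study. The sentence on stops does not repeat the restriction to partial dates, so a programmer might accept the Visit 1 entry as clear evidence of a stop. The text does not say so, and the sentences before it are about comparing dates.

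If a Visit 1 record counted as clear evidence of a start before first dose, (a) and (d) would become both Prior and Concomitant. Pattern (b) would become both, or Prior only where the record shows that the drug had stopped. Patterns (c) and (e) would not change.

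**The case against.** The best defence is that defaulting to concomitant is the cautious choice: when timing is uncertain, count the drug as on-study exposure. That is reasonable, but it only requires the drug to be counted as concomitant. The class both Prior and Concomitant does that equally well without denying earlier use that the Visit 1 entry documents.

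It can also be said that timing information should exist for most of these drugs, since eligibility turns on a stable dose or a washout and the sponsor reviews concomitant medication before approving entry. A month or year before first dose is enough under the present rule. This stands, and it may make the affected records few. It does not make the class right where the date is missing.

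Several stronger conclusions are tempting, and the documents do not support them:

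- **Distortion of the estimand.** A reader might infer this because SAP 4.6 lists concurrent treatments among the events handled by treatment policy. Those are absorbed whatever their label, and the model in SAP 5.1.1 has no medication term. The class enters no efficacy analysis.
- **Distortion of the secondary safety endpoint.** That endpoint is use of concomitant medication. A continuing background drug is concomitant and is counted so. Neither SAP 4.10 nor Protocol 9.3.10 plans a table of newly started drugs.
- **False prohibited use on study.** SAP 4.10 plans a summary of Protocol Table 2 drugs, and a stopped drug without usable dates could appear there. But Table 2 sets washouts before Screening, so timing has to be known for eligibility, and on-study prohibited use is handled separately through withdrawal and protocol deviations. This is a possibility, not a demonstrated result.
- **Every unknown start is misclassified.** Patterns (c) and (e) show otherwise.

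**Conclusion.** The point holds as a minor fault in a stated rule. For a drug recorded at Visit 1 as taken, with a start date that is missing or cannot be placed before first dose and no clear evidence of a stop before first dose, SAP 4.10 gives a class that contradicts Protocol section 6. SAP 5.5 says that the planned analysis does not differ from the protocol. The consequences are an on-study-start label, absence from the Prior summary and, for a drug already stopped but without usable dates, possible display as on-study use. Only descriptive tables and listings are touched; the primary analysis, estimand, alpha and sample size are not.

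The size cannot be derived, because the documents give no rate of unresolvable start dates. A reader might assume 1 to 2 background drugs for each of 188 participants with 5% to 20% of starts unknown, giving 188 × 1 × 0.05 ≈ 9 to 188 × 2 × 0.20 ≈ 75 records. Both inputs are guesses. The product also ignores records that a partial or stop date would place correctly, and it counts records where the tables count participants within ATC class. It should not be read as an estimate.

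The conclusion rests on reading the parenthesis about partial dates as naming the evidence allowed, which is its plain sense.

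**What to change.** Amend SAP 4.10 as follows:

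- A medication recorded at Visit 1, or recorded at Visit 2 as taken before first dose, counts as clear evidence of a start before first dose, whatever its start date.
- Class it as both Prior and Concomitant, or as Prior only if it is recorded as stopped before first dose.
- Keep the Concomitant only default for medications first recorded after first dose.

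This brings the SAP into line with Protocol section 6 and keeps the cautious on-study count. It does not settle drugs whose stop is truly unknown: without a record that they had stopped, they would still be counted as concomitant, but with the Prior label restored.

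The cost is one SAP sentence and minor programming. The eCRF is not among the documents, Protocol section 6 describes a concomitant medication log or page kept throughout the study, and Table 1 shows prior and concomitant medication as a single row. Nothing shows that the visit of first entry is stored for each record. The sponsor should therefore confirm which field, a recording visit or a prior/ongoing flag, identifies these records before the rule is programmed.
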